2. OVERVIEW (SYNOPSIS)

Sponsor: PROMOMED RUS LLC, Russia	Separate study table relating to part of the dossier	(For use by national authorized bodies only)
Name of finished product: Areplivir, film-coated tablets	Volume: Pages:	
Active ingredient: Favipiravir		
Protocol No.: FAV052020		
Clinical study name: Open randomized multicenter comparative study on the efficacy and safety of Areplivir film-coated tablets (PROMOMED RUS LLC, Russia) in patients hospitalized with COVID-19		
Investigators, Study site: The study is conducted at five research centers in the Russian Federation. Detailed information is provided in Section 6.		
Publication: A list of scientific papers and publications relevant to this study will be presented in the Clinical Study Final Report.		
Study period: Q2 2020 – Q4 2020	Drug development phase: III	
Study purpose: Assess the efficacy and safety of Areplivir versus standard therapy in patients hospitalized with COVID-19. Study objectives: 
 • Assess the efficacy of Areplivir versus standard therapy in patients hospitalized with COVID-19. • Assess the safety of Areplivir versus standard therapy in patients hospitalized with COVID-19. 		
Methodology: an open randomized multicenter comparative study on the efficacy and safety of Areplivir in patients hospitalized with COVID-19.		
Number of patients (planned and included in the analysis): The study will randomize 200 patients. Given the possible non-inclusion of patients at the screening stage, the maximum number of patients to sign the Informed Consent Form in the Patient Information Leaflet and to participate in screening can be no more than 210 people. This interim report is based on data on 80 patients (40 patients in the Areplivir arm + 40 patients in the standard therapy arm). Patients who met the inclusion criteria and did not meet the non-inclusion criteria were randomized to 2 groups (treatment arms) in a 1:1 ratio: Arm 1 (n=100) receives the study drug Areplivir film-coated tablets: on day 1 of therapy - 1600 mg (8 tablets) 2 times a day; on days 2-14 of treatment - 600 mg (3 tablets) 2 times a day. The drug is taken orally every 12 hours, swallowing whole tablet without chewing and washing down with a glass of water. The course of treatment is 14 days.		

Sponsor: PROMOMED RUS LLC, Russia	Separate study table relating to part of the dossier	(For use by national authorized bodies only)

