In case change of the planned endpoints, separate adjustment will be made for the multiplicity of comparisons and the required number will be recalculated at the second stage.

The total planned number of patients before the completion of the first stage will be 100 patients in each of the arms.

The estimated calculation until the data of the first stage are obtained is as follows. Given the available data from Chinese researchers, 15% superiority of favipiravir therapy over standard therapy without favipiravir is allowed in relation to the rate of improvement by 2 or more categories on categorical scale by day 10 of treatment. The adopted higher response to standard therapy of 70% is associated with a longer duration relative to the Chinese study (10 days instead of 7 days).

An RCT enrolling patients within 12 days of symptom onset found that favipiravir was superior to arbidol in terms of the clinical recovery rate at day 7 in patients with mild illness (62 [56%] of 111 with arbidol vs 70 [71%] of 98 with favipiravir), but not in those with critical illness (0 vs 1 [6%]). (Chen C. Huang J. Cheng Z. et al. Favipiravir versus arbidol for COVID-19: a randomized clinical trial. medRxiv. 2020; (published online April 15.) (preprint).

Tests for Two Proportions

Numeric Results for Testing Two Proportions using the Z-Test with Unpooled Variance

H0: $P_1 - P_2 \geq 0$ vs. H1: $P_1 - P_2 = D_1 < 0$.

Target	Actual	Diff						
Power	Power*	N1	N2	N	P1	P2	D1	Alpha
0.80170	107	107	214	0.6500	0.8000	-0.1500	0.0500	0.80

* Power was computed using the normal approximation method.

Thus, the minimum number of subjects required for a clinical study is 200 with 100 subjects randomized to each of the two groups.

Statistical analysis

The purpose of statistical analysis is to prove superiority of Areplivir, film-coated tablets (PROMOMED RUS LLC, Russia), over standard therapy in patients hospitalized with COVID-19.

The results of statistical analysis, descriptive statistics and illustrative tables, graphs, lists will be presented in interim and final clinical study reports.

General methods of analysis

Statistical analysis is carried out in accordance with the requirements of the Guideline for Good Clinical Practice (ICH 9) approved by the Eurasian Economic Commission, and other applicable requirements and laws.

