
Certified statistical software with validated algorithms is used to perform statistical analyses and to ensure proper documenting (StatSoft Statistica 10.0., IBM SPSS Statistics 22).
 
Descriptive statistics are provided for all efficacy and safety indicators collected during the study. Continuous (quantitative) data are presented using the number of observations, arithmetic mean value, confidence interval (CI) 95% for mean, standard (rms) deviation, median, interquartile span (25th and 75th centiles), minimum and maximum.
 
Ordinal, categorical and qualitative data are presented as absolute frequencies (number of observations), relative frequencies (percent) and 95% CI (unless otherwise stated).
 
The check for normality of distribution is carried out by one of the generally accepted methods (Shapiro-Wilk test, Kolmogorov-Smirnov test). For non-Gaussian distributions, non-parametric methods will be used to compare efficacy and safety indicators.
 
Significance levels and confidence intervals are calculated as bilateral, the statistical significance of differences is two-sided by default and refers to significance level 0.05 (unless specified otherwise).
 
Analysis of demographics and other source data
 
Demographic data (age, sex) and baseline condition data are presented along with summaries in the form of absolute frequencies (number of observations), relative frequencies (percent), or using the arithmetic mean, confidence interval (CI) 95% for mean, standard deviation, median, interquartile span (25th and 75th centiles), minimum and maximum, depending on the type of variable.
 
To test the study group homogeneity hypothesis, at the baseline zero hypotheses (no differences between groups) are tested with Student's t-test (for interval measures with normal distribution in the study population), Mann-Whitney's test (for ordinary measures or for interval measures with distribution different from normal) or Fisher's exact test and χ^2 test (for qualitative indicators). If statistically significant differences between study arms are found, the magnitude of differences is estimated using confidence intervals.
 
Analysis of primary efficacy parameter
 
Primary efficacy endpoints:
 
One of the primary efficacy parameters is the time (in days) to improvement of patient's clinical status according to the categorical ordinal scale of clinical improvement.
 
 • Time (in days) to improvement in clinical status on a categorical ordinal scale of clinical improvement. 
To compare the primary efficacy indicator between arms, the Student's t-test for independent samples is used. If the necessary assumptions about the normality of distribution of this indicator are not met, the non-parametric Mann-Whitney test will be used. Also, the Kaplan-Meier technique and compilation survival tables can be used as descriptive methods for studying this efficiency parameter. Gehan-Wilcoxon test, Cox-Mentel test or Log-Rank test can be used to compare the time (in days) to improve the clinical status of the patient between the study groups.
		

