
Sponsor: PROMOMED RUS LLC, Russia	Separate study table relating to part of the dossier	(For use by national authorized bodies only)
Name of finished product: Areplivir, film-coated tablets	Volume: Pages:	
Active ingredient: Favipiravir		

The proof of the superiority hypothesis is the establishment of a statistically significant time difference (in days) before patient's clinical status improvement between the Areplivir arm and the standard therapy arm.

The next primary efficacy parameter is the percentage of patients who achieved an improvement in clinical status according to the categorical ordinal scale of clinical improvement by 2 or more categories at Visit 3.

- Rate of clinical status improvement by categorical ordinal scale of clinical status improvement by 2 or more categories at Visit 3.

For the analysis of this parameter, an intergroup comparison of percentages is used using a two-sided version of the **Fischer's exact test** (or a two-sided version of the χ^2 (chi-square) test, if all the expected values in the cells of the contingency table for this analysis are 5 or more). The percentage of patients who achieved improvement in clinical status on a categorical ordinal clinical improvement scale by 2 or more categories at Visit 3 is presented with a two-sided 95% confidence interval by treatment arm. Hypothesis testing is performed at a 5% significance level. The difference in proportion between treatment arms and the 95% bilateral confidence interval for the difference in proportion calculated by **Newcomb-Wilson technique is presented**.

The proof of the hypothesis of superiority of Areplivir film-coated tablets (PROMOMED RUS LLC, Russia) is the establishment of a statistically significant difference in the proportions of patients who achieved an improvement in clinical status according to the categorical ordinal scale of clinical improvement by 2 or more categories at Visit 3, between Areplivir arm and standard therapy arm.

Analysis of the primary efficacy parameter is performed in the ITT population (main analysis), and in the PP population (additional analysis). A summary of all efficacy indicators is provided.

Analysis of secondary efficacy parameters

The following efficacy parameters in the protocol are represented by qualitative values:

- Percentage of patients with elimination * COVID-19 according to PCR analysis at Visit 3.
- Percentage of patients transferred to intensive care unit.

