- Incidence of serious adverse events (SAEs) associated with the use of the study drug/standard therapy;
- Percentage of patients with at least one AE;
- Percentage of patients who discontinuation treatment due to AE.

Cross-group comparisons are performed for all safety indicators. The comparison of groups on frequency indicators is carried out using the *Fischer's exact test* or the χ^2 (chi-square) test, depending on the expected value in the cells of contingency table. For quantitative laboratory results, comparisons between groups at relevant visits are made using the *Student's t-test* or the *Mann-Whitney test* (depending on the nature of the distribution of quantitative indicators).

For analysis of all safety parameters the safety population was used.

In case of developing acute respiratory distress syndrome and the need to switch patient to mechanical ventilation, the investigational drug is canceled, but the patient is not withdrawn from the study. Patients are under follow-up until Visit 6, the data are taken into account to assess efficacy in the ITT population.

Interim analysis

In the first stage, 40 patients were included in each group (study arm). Given 40 patients in each of the study arms, the sensitivity of the study to confirm 15% superiority by incidence, supposing the expected response 80% in the test drug arm, will exceed 45%.

Sponsor: PROMOMED RUS LLC, Russia	Separate study table relating to part of the dossier	(For use by national authorized bodies only)
Name of finished product: Areplivir, film-coated tablets	Volume: Pages:	
Active ingredient: Favipiravir		

Two Independent Proportions (Null Case) Power Analysis									
Numeric Results of Tests Based on the Difference: P1 - P2									
H0: P1 - P2 ≥ 0. H1: P1 - P2 = D1 < 0. Test Statistic: Z test with pooled variance									
		Sample Size	Sample Size	Prop H1	Prop				
		Grp 1	Grp 2	Grp 1 or	Grp 2 or	Diff	Diff	Target	Actu
	Power	N1	N2	Trtmnt	Control	if H0	if H1	Alpha	Alpha
				P1	P2	D0	D1		
	0.4553	40	40	0.6500	0.8000	0.0000	-0.1500	0.0500	0.0500

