
Said statistical power (45%) is acceptable for exploratory stages of the studies aimed to select the duration for endpoint monitoring and to select the endpoint at the second (confirming) stage. In case change of the planned endpoints, separate adjustment will be made for the multiplicity of comparisons and the required number will be recalculated at the second stage.
 
Significance level used in the clinical study Significance levels and confidence intervals are calculated as bilateral, the statistical significance of differences is two-sided by default and refers to significance level 0.05 (unless specified otherwise).
 
Stopping criteria for the clinical study This protocol does not contain any statistical criteria for stopping the clinical study.
 
Accounting for missing data, data not to be analyzed and questionable data In the case of for missing data, data not to be analyzed and questionable data, appropriate statistical analysis methods are applied. Patients who will not be able to complete the course of therapy according to the protocol are included in the analysis of the main endpoint using the last observation carried forward (LOCF) method. This means that measures taken as criteria for efficacy will be assessed for such patients at the time of dropping out of the study.
 
Procedures for reporting any deviations from the original statistical plan All deviations from the final version of the statistical analysis plan will be described and substantiated in the final clinical study report.
 
Population analysis The statistical analysis includes the following patient populations:
 
 Safety population: patients who have received at least one dose of the study drug and for whom there is an assessment of condition and/or AE for at least one time point after administration. Population of all patients included in the study (Intent-to-treat, ITT): patients who received at least one dose of the drug in the study and for whom there is data for at least one visit after the baseline (Visit 0). Population of patients who completed the study as per the Protocol (Per protocol, PP): patients who have completed the study as per the Study Protocol. 
In case of developing acute respiratory distress syndrome and the need to switch patient to mechanical ventilation, the investigational drug is canceled, but the patient is not withdrawn
									

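### Safety versus standard therapy is compared by significance tests alone; adding the between-arm difference with its 95% CI would show how much excess harm is not ruled out

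*Combined protocol and SAP*

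**What the plan says.** The Study objectives list two aims. The second is: "Assess the safety of Areplivir versus standard therapy in patients hospitalized with COVID-19".

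Under Safety Analysis the between-arm plan reads: "Cross-group comparisons are performed for all safety indicators. The comparison of groups on frequency indicators is carried out using the" Fisher's exact test or the chi-square test, chosen by the expected cell counts. Laboratory values are compared by Student's t-test or Mann-Whitney. The section names no risk difference or ratio, and no interval for either. The default for all tests is that "the statistical significance of differences is two-sided by default and refers to significance level 0.05".

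Two other places bear on the point:

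- General methods of analysis promises descriptive statistics for every safety indicator, with counts, percentages and a 95% CI for categorical data. These intervals describe a frequency, not a difference between arms.
- Analysis of primary efficacy parameter plans, for the Visit 3 improvement rate, the difference in proportions and a 95% "bilateral confidence interval for the difference in proportion calculated by" the Newcombe-Wilson method. No safety proportion gets this.

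The section on demographics and other source data estimates the magnitude of a difference by confidence interval when a test is significant. That rule is written for baseline comparisons only.

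**The concern.** A comparative safety objective needs an estimate of how much more harm one arm may carry than the other. The only between-arm result that the plan specifies is a p-value. With 40 or 100 patients per arm and uncommon events, p will often exceed 0.05 whether or not there is a real excess. The interim report on 80 patients and the final report could then meet the safety objective with a statement of no significant difference, and no figure for the excess that the data still allow. The plan already has the right summary and uses it for efficacy.

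**Working it through.** **Inputs from the documents.** There are 100 per arm at the end ("Thus, the minimum number of subjects required for a clinical study is 200 with 100 subjects randomized to each of the two groups") and 40 per arm at the first stage ("Given 40 patients in each of the study arms, the sensitivity of the study to confirm 15% superiority by incidence"). Tests are two-sided at 0.05. The test is chi-square if all expected counts are 5 or more, otherwise Fisher's exact. The threshold of 5 is stated in the efficacy sections; Safety Analysis refers to expected counts without a number, so I carry it over.

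**Input assumed.** The documents give no rate for any adverse event and no power for safety. I take a tripling from 1%, 2% or 5% in the standard therapy arm.

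**The plan's own power figures.** These concern efficacy and only check the method.

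- 65% vs 80%, 107 per arm, unpooled Z, one-sided 0.05: power = Φ(0.15/√[(0.65×0.35 + 0.80×0.20)/107] − 1.645) = 0.8017. The plan states 0.80170.
- 65% vs 80%, 40 per arm, one-sided pooled Z, exact enumeration of two binomials: 0.4553, as stated. The normal approximation gives 0.4425.

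Both tables use one-sided hypotheses ("H0: P1 - P2 ≥ 0. H1: P1 - P2 = D1 < 0. Test Statistic: Z test with pooled variance"), whereas the safety tests are two-sided.

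**Chance that the planned test is non-significant.** For every pair of counts (x, y), take the product of the two binomial probabilities, apply the planned test, and sum the probabilities of the pairs with p < 0.05. That sum is the power, and one minus it is the chance of a non-significant result.

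| True rates (assumed) | 100 per arm | 40 per arm |
|---|---|---|
| 1% vs 3% | 1 − 0.034 = 97% | 1 − 0.001, over 99% |
| 2% vs 6% | 1 − 0.198 = 80% | 1 − 0.015 = 98.5% |
| 5% vs 15% | 1 − 0.682 = 32% | 1 − 0.222 = 78% |

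For 80% power at 2% vs 6%, the pooled normal approximation gives about 376 per arm. The limit is therefore the size of the trial.

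**What the interval adds.** With Wilson limits (l, u) for each arm and d = p1 − p2, the Newcombe-Wilson limits are d − √[(p1 − l1)² + (u2 − p2)²] and d + √[(u1 − p1)² + (p2 − l2)²].

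- 7/100 vs 2/100. The Wilson limits are 0.0343 to 0.1375 and 0.0055 to 0.0700. Lower limit: 0.05 − √(0.0357² + 0.0500²) = −0.011. Upper limit: 0.05 + √(0.0675² + 0.0145²) = +0.119. The difference is +5.0 points (CI −1.1 to +11.9). The expected count is 4.5 per arm, so Fisher's test applies: p = 0.17.
- 2/100 vs 2/100. The limits are ±√(0.0500² + 0.0145²) = ±0.052. Here p = 1.0, yet an excess of up to 5.2 points is not excluded.
- 3/40 vs 1/40. Here p = 0.62, and an excess of up to 17.5 points is not excluded.
- 6/100 vs 2/100. Fisher p = 0.28, CI −1.9 to +10.6. The interval includes zero, so it does not flag a harm that the test missed. It states what remains possible.

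**The case against.** Most of the case on the other side is sound, and it limits the point.

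- **A reader might infer that omitting the interval causes harms to be missed.** It does not. The miss rates come from sample size and event rate, and would be the same with the interval reported.
- **A reader might infer that safety has no upper bound at all, or that the test discards the data.** General methods of analysis plans 95% CIs for the frequencies. For 6/100 the Wilson interval is 2.8% to 12.5%. Counts and percentages are reported, so a reader could work out the difference for any patient-level proportion. Only the planned estimate of the difference, with its bound, is absent.
- **A reader might infer that the plan treats p > 0.05 as proof of safety.** It nowhere says so. Its rules of proof concern efficacy superiority only. It makes no safety non-inferiority claim either, so the lack of a safety margin is not an error.
- **The 80% figure is one assumed case.** It needs its rates and range beside it. For 5% vs 15% at 100 per arm the figure is 32%.
- **The text is a synopsis.** It refers to a final version of the statistical analysis plan, and silence in a synopsis is weaker evidence than silence in a full plan.

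What remains is that the comparison named in the objective has no planned estimate, although the same text specifies one for the Visit 3 rate.

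**Conclusion.** The point holds as a cheap improvement to reporting. It does not put the primary analysis in doubt. Safety versus standard therapy is a stated objective, and the documents plan only significance tests between arms for it. At 100 per arm, a true tripling would be non-significant with probability from 97% (1% vs 3%) through 80% (2% vs 6%) to 32% (5% vs 15%). At 40 per arm the range is from over 99% to 78%. These figures rest on assumed event rates, on the test-selection threshold of 5 and on two-sided 0.05. The missing interval itself does not depend on the assumed rates.

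**What to change.** In Safety Analysis, keep the tests and add an estimate beside each. For each patient-level safety proportion as the plan defines it (at least one AE, at least one adverse drug reaction, at least one treatment-associated SAE, discontinuation of treatment due to AE), report the difference, Areplivir minus standard therapy, with the Newcombe-Wilson 95% CI already specified for the Visit 3 rate. Read the upper limit as the excess harm not ruled out. Add one sentence: a non-significant test will not be reported as absence of a safety difference. Apply this to both the interim and the final report.

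The cost is SAP wording and a few table columns, with no extra patients or data. The downside is that wide intervals, especially at 40 per arm, will make the safety statement look less favourable than a bare report of no significant difference.

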
(with past history of: hysterectomy, tubal ligation, infertility, menopause more than 1 year).
 
or
 
 – men with preserved reproductive function who use barrier contraceptives, as well as men with infertility or vasectomy in the past medical history. 
Non-inclusion criteria:
 
 1. Hypersensitivity to favipiravir and/or other components of the study drug. 2. Impossibility of CT procedure (for example, gypsum dressing or metal structures in the field of imaging). 3. The need to use drugs from the list of prohibited therapy. 4. Need for treatment in the intensive care unit. 5. Impaired liver function (AST and/or ALT ≥ 2 UNL and/or total bilirubin ≥ 1.5 UNL) at the time of screening. 6. Impaired kidney function (creatinine clearance according to Cocroft-Gault formula less than 45 ml/min) at the time of screening. 7. Positive testing for HIV, syphilis, hepatitis B and/or C. 8. Chronic heart failure FC III-IV according to New York Heart Association (NYHA) functional classification. 9. Malabsorption syndrome or other clinically significant gastrointestinal disease that may affect absorption of the study drug (non-correctable vomiting, diarrhea, ulcerative colitis, and others). 10. Malignancies in the past medical history. 11. Alcohol, pharmacological and/or drug addiction in the past medical history and/or at the time of screening. 12. Schizophrenia, schizoaffective disorder, bipolar disorder, or other history of mental pathology or suspicion of their presence at the time of screening. 13. Severe, decompensated or unstable somatic diseases (any disease or condition that threaten the patient's life or impair the patient's prognosis, and also make it impossible for him/her to participate in the clinical study). 14. Any history data that the investigating physician believes could lead to complication in the interpretation of the study results or create an additional risk to the patient as a result of his/her participation in the study. 15. Patient's unwillingness or inability to comply with procedures of the Study Protocol (in the opinion of physician investigator). 16. Pregnant or nursing women or women planning pregnancy. 17. Participation in another clinical study for 3 months prior to inclusion in the study. 18. Other conditions that, according to the physician investigator, prevent the patient from being included in the study. 		

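### Laboratory safety results are compared visit by visit without the patient's own baseline value: valid under randomisation, but less precise than the data already collected allow

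*Combined protocol and SAP*

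**What the plan says.** All of the following is in the synopsis (section 2) of the combined protocol and SAP.

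- **Safety Analysis.** "Cross-group comparisons are performed for all safety indicators". For continuous laboratory data the rule is: "For quantitative laboratory results, comparisons between groups at relevant visits are made using the" t-test or the Mann-Whitney test, the choice "depending on the nature of the distribution of quantitative indicators". The analysis set is the safety population.
- **Baseline in that comparison.** None is named. For laboratory data there is no covariate, change from baseline, repeated-measures model or shift table. No effect estimate or interval is asked for in the laboratory comparison.
- **Baseline elsewhere.** The section on demographics and other source data tests the arms for baseline differences and puts confidence intervals on any that are significant. It carries nothing into a later comparison.
- **Baseline values are available.** One non-inclusion criterion is "Impaired liver function (AST and/or ALT ≥ 2 UNL and/or total bilirubin ≥ 1.5 UNL) at the time of screening". The next sets a limit on creatinine clearance, also at screening.
- **Attendance.** Under Duration of the study, patients discharged early need not come to the site for Visits 5 and 6, and Visit 4 is held at discharge for Arm 2 patients who leave earlier.

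**The concern.** A patient's liver enzymes, bilirubin or creatinine at a follow-up visit usually depend in part on where that patient started. A test that looks only at the follow-up value leaves this stable between-patient variation in the error term. It also lets a fraction of any chance baseline difference between the arms, equal to the baseline-to-visit correlation, into the observed contrast.

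Safety is one of the two stated objectives, and this is the only between-arm analysis of continuous laboratory values that the synopsis describes. For a safety comparison the costly error is to report no significant difference when there is a real shift. The plan makes that error somewhat more likely than it needs to be.

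A smaller point goes with it. Because the distribution decides the test, one analyte can be compared on means at one visit and on ranks at the next, which makes the series of results hard to read together.

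**Working it through.** **The plan's own figures.** The documents give no power for any laboratory comparison. Their two power figures concern the efficacy proportion (0.65 against 0.80) and both reproduce as one-sided calculations at 0.05. Exact enumeration of the pooled Z test with 40 per arm gives 0.4553, as stated. The unpooled Z test with 107 per arm gives 0.8017, as stated. Neither bears on laboratory data.

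**Inputs from the documents**
- Patients per arm, n: 100 planned, 40 at stage 1, allocation 1:1.
- Significance level: 0.05, two-sided by default, so the critical value is 1.96.

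**Inputs assumed, because the documents do not give them**
- True shift in the laboratory value, d: 0.35 SD of the follow-up value.
- Correlation between baseline and follow-up value, r: 0.3 to 0.7.

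**Formulas**
- ANCOVA on baseline multiplies the residual variance by 1 − r².
- Power ≈ Φ( d·√(n/2) / √(1 − r²) − 1.96 ). Setting r = 0 gives the unadjusted test.

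**Variance.** 1 − 0.3² = 0.91, 1 − 0.5² = 0.75, 1 − 0.7² = 0.51. The reduction is 9%, 25% and 51%.

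**Power with 100 per arm having data.** d·√(n/2) = 0.35 × √50 = 2.475.
- Unadjusted: Φ(2.475 − 1.96) = Φ(0.515) = 0.70
- r = 0.3: Φ(2.475/0.954 − 1.96) = Φ(0.634) = 0.74
- r = 0.5: Φ(2.475/0.866 − 1.96) = Φ(0.898) = 0.82
- r = 0.7: Φ(2.475/0.714 − 1.96) = Φ(1.506) = 0.93

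**Power with 40 per arm.** d·√(n/2) = 0.35 × √20 = 1.565. Unadjusted 0.35; 0.37 at r = 0.3, 0.44 at r = 0.5, 0.59 at r = 0.7.

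**Detectable shift.** With 100 per arm and 80% power, the smallest detectable shift falls from 0.396 SD unadjusted to 0.378 SD (r = 0.3), 0.343 SD (r = 0.5) and 0.283 SD (r = 0.7).

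**Gain as patients.** Adjustment is worth n/(1 − r²) − n extra patients per arm. With n = 100 that is about 10, 33 and 96 at r = 0.3, 0.5 and 0.7. With n = 40 it is about 4, 13 and 38. The gain on this measure shrinks in proportion to the number with data, so it is smaller at visits that discharged patients skip.

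**Chance imbalance.** The standard error of the difference in baseline means is √(2/n) SD: 0.14 SD with 100 per arm and 0.22 SD with 40. Only a fraction r of a realised difference reaches the follow-up contrast.

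**Would change from baseline do instead?** Its variance factor is 2(1 − r), which is below 1 only when r exceeds 0.5. At r = 0.3 the factor is 1.4, worse than ignoring baseline. ANCOVA's factor never exceeds 1.

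**The case against.** The strongest objection is that nothing here is an error. Patients "were randomized to 2 groups (treatment arms) in a 1:1 ratio", so a visit-wise t or Mann-Whitney comparison is valid for patients with data, and chance baseline imbalance is already reflected in its standard error. That stands. A reader might infer that the planned comparison is biased, or that a baseline imbalance passes into it in full. The documents support neither.

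Other objections stand in part:

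- **Peripheral target.** Laboratory values are not among the five listed safety criteria, the trial is not sized for them, and an important abnormality could also be captured as an adverse event. This lowers the priority but does not remove the gain.
- **Assumed inputs.** The 0.35 SD shift and the correlations are not in the documents. A reader might quote only the upper part of the range, 82% to 93%, but nothing justifies leaving out r = 0.3. The eligibility limits narrow the baseline range, and acute illness may weaken the correlation further. The formula is a normal approximation, not a calculation for Mann-Whitney on skewed analytes.
- **Attendance.** The 100 per arm is optimistic for Visits 5 and 6. Selective attendance may threaten those comparisons more than a missing covariate does, and adjustment does not cure it.
- **Isolated extremes.** ANCOVA gains power for a shift in the mean. A harm that shows as a few very high values needs another display.
- **Stage 1.** The synopsis already describes an interim report on 80 patients, so any gain there would come from a re-analysis.
- **Scope of the text.** This is a synopsis. It does not expressly exclude testing changes, and it refers to a final SAP that may say more. On its plain reading, results at visits are compared and baseline is not used.

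**Conclusion.** The point holds as one of efficiency. The planned laboratory comparison is valid under randomisation but less precise than it could be, because it sets aside baseline values that the trial already measures for liver and kidney function.

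The direction follows for any non-zero baseline correlation, apart from the negligible loss of one degree of freedom. The size depends on the assumptions set out above: across the assumed range, the gain with 100 per arm runs from slight (four points of power at a correlation of 0.3) to substantial (more than 20 points at 0.7).

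The documents do not support the stronger inference that the laboratory safety conclusions would be invalid, or that the trial as planned cannot detect laboratory harm. This is a low-priority improvement at almost no cost. It leaves selective attendance after discharge and isolated extreme values unresolved.

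**What to change.** For the final analysis, replace the laboratory sentence in the Safety Analysis section with the following:

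- At every visit, compare the arms by ANCOVA of the laboratory value on arm and the patient's own baseline value.
- Fix the scale for each analyte in advance, for example log for AST, ALT and bilirubin. Do not let a normality test choose the method, and do not keep a rank version in reserve for when normality fails; either would bring back the data-driven choice.
- Report the adjusted difference, or the ratio for log-scale analytes, with its 95% CI and the number of patients with data per arm.
- Label any application to the stage 1 data already reported as a re-analysis.

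The cost is one degree of freedom, a few sentences of SAP text and some programming. The screening liver and kidney values are already collected, so no new visit or sample is needed for them.
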